### 12. MEDICAL HISTORY

Medical History information will be presented for the SAF. Medical History conditions are defined as those conditions which stop prior to study drug administration. Medical History will be coded using the Medical Dictionary for Regulatory Activities (MedDRA) central coding dictionary version 26.1.

- Presented by System Organ Class (SOC) and Preferred Term (PT) and all participants combined.
- The number and percentage of participants with at least one condition in each SOC and each PT will be summarized by treatment group.
- By treatment, each participant's medical history will be listed with SOC and PT.

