8.4.1 Time Period and Frequency for Collecting AE and SAE Information

All AEs and SAEs will be collected from the signing of the ICF until the last visit as specified in the Schedule of Assessments (Table 1.3-1).

Medical occurrences that begin before the start of study intervention but after obtaining informed consent will be recorded as Medical History / Current Medical Conditions, not as AEs.

All SAEs will be recorded and reported to the sponsor or designee immediately and under no circumstance should this exceed 24 hours, as indicated in Section 10.3. The investigator will submit any updated SAE data to the sponsor within 24 hours of it being available.

Investigators are not obligated to actively seek information on AEs or SAEs after conclusion of the study participation. However, if the investigator learns of any SAE, including a death, at any time after a participant has been discharged from the study, and he/she considers the event to be reasonably related to the study intervention or study participation, the investigator must promptly notify the sponsor.

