9.2.7.3 Analysis of Demographic and Baseline Characteristics

Demographic and anthropometric variables (age, sex, ethnicity, race, height, weight, and body mass index) will be listed for each participant. Demographic characteristics (age, sex, ethnicity, and race) and anthropometric characteristics (height, weight, and body mass index) will be summarized by treatment group and for all participants in the safety population.

Medical history data will be listed for each participant including visit, description of the disease/procedure, MedDRA system organ class, MedDRA preferred term, start date, and stop date (or ongoing if applicable).

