### 18.1. Adverse Events

Definitions of AE, unsolicited AE, and solicited AE can be found in Section 10.3 of the clinical study protocol. Unsolicited Adverse Events (AEs) will be coded using MedDRA central coding dictionary, version 26.1.

Treatment-emergent adverse events (TEAEs) are defined as AEs that first occur or worsen in severity after the study medication administration, and up to Day 71 (including the follow-up period) after the study medication administration.

Pretreatment AEs are defined as AEs occurring prior to dosing. These events will be presented in the listings only and will not be included in the tabular summary of AEs.

See Appendix 2 for handling of partial dates for AEs. In the case where it is not possible to define an AE as treatment emergent or not, the AE will be classified by the worst case, i.e., treatment emergent. Solicited AEs are predefined local injection site reactions and systemic events for which the participant is specifically questioned, and responses recorded in the eCRF data. These are collected at predefined timepoints of 1 and 4 hours post dose (Day 1), 24 hours post dose (Day 2), and on Days 3 and 29 for tenderness, pain, erythema/redness, and induration/swelling with responses based on the severity of each condition as Mild, Moderate, Severe, or Potentially Life-threatening.

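### SAP section 12 limits medical history to conditions that ended before dosing, so its summary leaves out conditions still ongoing at dosing, contrary to the protocol

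*SAP*

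**What the plan says.** **SAP section 12 (Medical History).** The definition is "Medical History conditions are defined as those conditions which stop prior to study drug administration". The section then plans a summary of participants by system organ class and preferred term, and a listing by treatment in which "each participant's medical history will be listed with SOC and PT". Both use the term just defined.

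**SAP section 10.** Medical history is named among the baseline characteristics to be listed for each participant. The restriction to ended conditions is not repeated.

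**Protocol section 9.2.7.3.** Medical history is to be listed, and the fields include "start date, and stop date (or ongoing if applicable". The protocol plans no summary table for it.

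**Protocol section 8.4.1.** One sentence says "All AEs and SAEs will be collected from the signing of the ICF until the last visit". The next paragraph says that anything arising between consent and dosing "will be recorded as Medical History / Current Medical Conditions, not as AEs".

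**SAP section 18.1.** Treatment-emergent events are "AEs that first occur or worsen in severity after the study medication administration". A separate, listing-only category is also defined: "Pretreatment AEs are defined as AEs occurring prior to dosing".

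**The concern.** A condition present at dosing is the most useful part of a medical history when a post-dose event is read: it shows whether the event is new, a continuation or a worsening. The SAP definition removes that part and keeps only what had already ended. The protocol's listing expects an ongoing status to appear, and under the SAP 12 definition it never could.

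The context matters in this trial. The protocol presumes that adverse events are related to study intervention unless another cause is evident (sections 8.4 and 10.3.4), and section 10.3.4 names underlying disease among the alternative causes to weigh. With 7 active participants per cohort, the safety data are read largely participant by participant. Participants with stable, mild conditions can be enrolled: exclusion criterion 1 bars serious or unstable disorders, and criterion 8 allows topical medications and over-the-counter anti-inflammatory drugs.

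**Working it through.** No figure is involved, so the check classifies each kind of pre-dose condition under the rules of both documents.

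| Condition | Protocol | SAP 12 summary | Adverse-event outputs |
|---|---|---|---|
| A. Ended before dosing (onset before or after consent) | Medical history, with stop date | Included | For onset after consent, pretreatment listing only if recorded as an AE |
| B. Onset before consent, ongoing and stable at dosing | Medical history, shown as ongoing (9.2.7.3) | Excluded | None |
| C. Onset after consent, ongoing and stable at dosing | Medical history or current condition, not an AE (8.4.1, later sentence) | Excluded | Pretreatment listing only if the site recorded it as an AE |
| D. Ongoing at dosing, worsens afterwards | Medical history, and the exacerbation is an AE (10.3.1) | Baseline condition excluded | The worsening is a TEAE (SAP 18.1) |

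**Rows B to D, SAP 12 summary.** A condition that is ongoing at dosing has not stopped before dosing, so it fails the definition. This holds whatever its onset date.

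**Rows B and C, adverse-event outputs.** SAP 18.1 requires first occurrence or worsening after dosing. SAP Appendix 2 classes an event with a known start date before the dosing date as not treatment-emergent. A stable condition therefore does not enter the TEAE tables, which is correct. It does mean that those tables cannot stand in for the missing baseline information.

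**Is the narrowing declared?** The readable part of SAP section 3.3, which lists departures from the protocol, does not mention it. One bullet there is redacted, so it can be said only that no visible text declares it.

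**Is there another home for ongoing conditions?** No readable section plans a concurrent-conditions output. SAP section 19 names only comments as not presented, so nothing announces a deliberate omission. SAP section 13 defines both prior and concomitant medications; for conditions, only the counterpart of prior exists.

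**Protocol 8.4.1 against SAP 18.1.** If the collection sentence governs, events between consent and dosing are recorded as AEs and the SAP's pretreatment category has content. If the later sentence governs, they are not AEs and the category has nothing to list. The documents do not say which prevails.

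**The case against.** The strongest reply is that ongoing conditions may well be reported despite SAP 12. SAP 10 promises a medical-history listing without the restriction, the protocol listing asks for ongoing status, and output content is set by templates supplied with the SAP that are not available here. This stands. A reader might infer that ongoing conditions appear in no planned output at all, but the documents do not establish that. The omission is firm for the SAP 12 summary and conditional for the listing.

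Nor is the summary wrong against a protocol table, because the protocol plans only a listing. The summary is incomplete relative to what the protocol treats as medical history.

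Three further inferences are tempting and also fail:

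- *Conditions ongoing at dosing escape safety reporting.* They do not if they worsen. Exacerbation is an AE under protocol 10.3.1 and a TEAE under SAP 18.1. A condition first detected after dosing is also an AE, even if it was present earlier.
- *The definition hides alternative causes when causality is judged.* The investigator makes that judgment from the source documentation and must consider underlying disease (protocol 10.3.4). The SAP's final outputs come after database lock, and SMC reporting is outside its scope. Concomitant medications are also listed with their indication (protocol 9.2.7.4).
- *The pretreatment-AE listing must be empty and pre-dose SAEs have no status.* The listing is empty only if the later sentence of 8.4.1 prevails. SAEs are collected from consent under 8.4.1, and section 5.3 requires any SAE to be captured for screen failures. What is missing is one stated place of recording.

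None of this reconciles the SAP 12 definition with the protocol.

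**Conclusion.** The conflict is real and its consequence is limited. As written, the SAP 12 summary excludes all conditions ongoing at dosing, and the SAP 12 listing does too if the same definition is applied. No primary safety count is shown to change. The loss is baseline context for interpreting post-dose events in the study report.

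The number of participants affected depends on their histories. The documents give nothing to narrow it within the roughly 54 planned participants (6 cohorts × 9), so it could be none or many.

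The conclusion assumes that SAP 12 is programmed literally, that the redacted bullet in SAP 3.3 and the unseen templates do not already resolve it, and that a worsening is entered with its own onset date, as Appendix 2 needs for it to count as treatment-emergent.

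The tension between protocol 8.4.1 and SAP 18.1 is a separate, lesser point about where pre-dose events are recorded.

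**What to change.** **Main change.** In SAP section 12, define medical history as conditions that started before study drug administration, whether resolved or ongoing, and carry an ongoing-at-dosing flag in both the summary and the listing. This aligns SAP 12 with SAP 10 and protocol 9.2.7.3. If the narrower definition was intended, declare it in SAP 3.3 and add an output for conditions present at dosing.

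**Secondary change.** Reconcile the two sentences of protocol 8.4.1 with each other and with the pretreatment category in SAP 18.1, so that events and SAEs between consent and dosing have one stated place of recording and reporting.

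**Cost.** One sentence and one flag in the SAP, with matching template edits, and one clarification in the protocol. On the protocol's wording, the start date and the stop date or ongoing status are already available for the listing, so the main change needs no new data.

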Signs, symptoms, or the clinical sequelae of a suspected overdose of either study intervention or a concomitant medication. Overdose per se will not be reported as an AE/SAE unless it is an intentional overdose taken with possible suicidal/self-harming intent. Such overdoses should be reported regardless of sequelae.

Events not Meeting the AE Definition

Medical or surgical procedure (eg, endoscopy, appendectomy): the condition that leads to the procedure is the AE.

Situations in which an untoward medical occurrence did not occur (social and/or convenience admission to a hospital).

Anticipated day-to-day fluctuations of pre-existing disease(s) or condition(s) present or detected at the start of the study that do not worsen.

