### 10. DEMOGRAPHIC AND OTHER BASELINE CHARACTERISTICS

Individual participant demographics and baseline characteristics (medical history and results from drug and alcohol screens, serology screening, and pregnancy tests) will be presented in listings.

Demographic characteristics such as age, sex, race, ethnicity, height, weight, and body mass index (BMI) will be summarized and tabulated by treatment, for all active-treated participants, for Japanese and non Japanese participants, and for all participants overall for the safety analysis set. Descriptive statistics will be presented for age, height, weight, and BMI. Frequency counts and percentages will be presented for sex, race, ethnicity, and if the participant belongs to the Japanese or to the non-Japanese group. No statistical testing will be carried out for demographic or other baseline characteristics.

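### SAP 12 limits medical history to conditions that stopped before dosing, so conditions ongoing at dosing drop out of its table and, on the SAP's only definition, out of its listing

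*SAP*

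**What the plan says.** SAP Section 12 presents medical history for the safety analysis set and defines it: "Medical History conditions are defined as those conditions which stop prior to study drug administration". Two outputs follow in the same section. The table is described as "The number and percentage of participants with at least one condition in each SOC and each PT will be summarized by treatment group". The listing is described as "By treatment, each participant's medical history will be listed with SOC and PT".

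SAP Section 10 mentions medical history separately, among the individual data to be listed: "baseline characteristics (medical history and results from drug and alcohol screens, serology screening, and pregnancy tests) will be presented in listings". It gives no definition of its own and does not repeat the restriction.

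Protocol 9.2.7.3 plans a listing only. The items to be listed include "MedDRA system organ class, MedDRA preferred term, start date, and stop date (or ongoing if applicable". Protocol 8.4.1 says that occurrences that begin after consent but before study intervention "will be recorded as Medical History / Current Medical Conditions, not as AEs".

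The visible entry in SAP 3.3 (changes from the protocol) concerns disposition; one further bullet is redacted. SAP 19 (data not presented) names only comments.

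**The concern.** The definition keeps the resolved conditions and drops those present when the participant was dosed. For a baseline description this is the wrong way round, because the conditions present at dosing bear most on how later events are read.

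Protocol 10.3.1 counts the exacerbation of a pre-existing condition as an adverse event, and protocol 10.3.4 asks for underlying disease to be considered as an alternative cause. In this first-in-human study, events are presumed related unless another cause is obvious. A reader of the study report who wants to check those judgments would look to the medical history outputs for what each participant already had. The table would also make each dose group look freer of current conditions than it was.

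**Working it through.** No figure in the plan bears on this point, so the check sets the sections side by side.

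1. **Apply the SAP 12 definition.** A condition with onset before dosing is either resolved before dosing or ongoing at dosing. The resolved one meets the definition. The ongoing one has not stopped before dosing and fails it. All conditions of the second kind are therefore excluded, whatever their number.

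2. **Table (SAP 12).** It counts participants with at least one condition, using the term just defined. It omits conditions ongoing at dosing.

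3. **Listing (SAP 12 against protocol 9.2.7.3).** The protocol calls for "start date, and stop date (or ongoing if applicable". Under SAP 12, no listed condition could be ongoing at dosing, so that entry could never apply to a condition present at dosing. The two texts do not agree.

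4. **Recording (protocol 8.4.1).** Occurrences between consent and dosing go to history or current conditions, with no requirement that they have stopped. The protocol's category is wider than the SAP's.

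5. **Is there another home for ongoing conditions?** SAP 10 lists medical history without the restriction, but the SAP's only definition of the term is in Section 12. No visible section defines an output for current conditions. SAP 13 handles the parallel problem for medications with two categories, prior and concomitant; Section 12 has only the equivalent of the first. A stable ongoing condition does not reach the adverse event outputs either, because protocol 10.3.1 lists among the things that are not adverse events: "Anticipated day-to-day fluctuations of pre-existing disease(s) or condition(s) present or detected at the start of the study that do not worsen".

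6. **Is the restriction declared?** It is not in the visible part of SAP 3.3, and SAP 19 does not name ongoing conditions among data not presented. The redacted bullet in 3.3 cannot be checked.

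7. **Scale of one omission.** The documents give no prevalence of ongoing conditions, so no count of affected participants follows. What can be shown is the weight of a single omitted participant in a table row, at planned enrolment and if nothing else puts that participant in the same row:
   - one dose group of 7: 1/7 = 14.3 percentage points
   - pooled placebo, 6 × 2 = 12: 1/12 = 8.3 points
   - all participants, 54: 1/54 = 1.9 points

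8. **Effect on endpoints.** Treatment emergence (SAP 18.1 and Appendix 2) is derived from dates and worsening in severity, not from the medical history outputs. No primary endpoint calculation changes.

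**The case against.** The best reply is that this is a loosely worded sentence with little practical effect. Its parts differ in weight.

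- **The listing may be complete after all.** SAP 10 commits to listing medical history with no restriction, the protocol specifies the ongoing entry, and the output templates mentioned in SAP 8 are not among the documents. A programmer could list every record. This stands in part: omission from the listing is not certain. But the only definition points the other way, and two readings of one listing are themselves a reason to reword.

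- **The table does not breach the protocol.** This stands. The protocol plans only a listing. A reader might infer that the table is also contrary to the protocol; it is not. The table's fault is that it inherits a definition that makes it incomplete.

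- **A pre-dose event need not vanish.** A reader might infer that, for example, a headache that starts on Day -1 and continues through dosing would appear in no output. The documents do not establish that. Protocol 8.4.1 opens by collecting adverse events from consent, and SAP 18.1 lists pretreatment adverse events, so the headache would be listed if the site recorded it as an adverse event. Medication indications (protocol 9.2.7.4) and the physical examination shift table (SAP 18.5) may also show traces of ongoing conditions. None of these is an output designed to show them.

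- **Safety judgments do not use these outputs.** This stands. Investigators judge novelty and relatedness during the study from source information. A reader might infer that adverse event classification is compromised; nothing in the documents supports that. What is lost is context for a reader of the report.

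- **Healthy volunteers have few ongoing conditions.** The entry criteria do point towards few: healthy on medical evaluation, no serious or unstable disorder, most medication barred. They do not exclude stable minor conditions, and permitted topical medications and over-the-counter analgesics suggest that some will occur.

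**Conclusion.** The inconsistency is real and lies in the text. Read literally, SAP 12 removes every condition ongoing at dosing from its table and, under the SAP's only definition, from its listing. The conflict with the protocol concerns the listing, where SAP 10 leaves the SAP ambiguous at best.

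The consequence is an incomplete baseline description and less context for telling new events from exacerbations. Any estimate of the number of participants affected would rest on a prevalence that the documents do not supply.

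The conclusion assumes that Section 12 is programmed as written, that sites follow the recording rule in protocol 8.4.1, and that the redacted bullet in SAP 3.3 does not declare the restriction. The SAP should be corrected, but nothing in the main safety analysis depends on it.

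**What to change.** Reword the definition in SAP 12, for example: *Medical history comprises all conditions with onset before study drug administration, whether resolved or ongoing at dosing; the listing shows start date and stop date or ongoing.* SAP 10 and SAP 12 then describe the same listing, and both agree with protocol 9.2.7.3 and 8.4.1.

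Tabulating resolved and ongoing conditions separately would help readers but is optional; the protocol does not ask for it.

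If the restriction is intended, declare it in SAP 3.3 and add an output for ongoing conditions.

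The cost is one SAP sentence. No new data should be needed, since the protocol's listing already calls for ongoing status; the case report form is not among the documents, so this should be confirmed.

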# 13. PRIOR AND CONCOMITANT MEDICATIONS

Prior and concomitant medications will be presented for the SAF. All medications will be coded using World Health Organization's WHODrug Global B3 dictionary version Sep2023. Medications will be listed

Visterra Insert
Customer Name/ Logo
Protocol VIS954-101
Page 24 of 42

Statistical Analysis Plan

and summarized by treatment and Anatomical Therapeutic Chemical (ATC) Level 3 classification.

See APPENDIX 2 for handling of partial dates for medications, in the case where it is not possible to define a medication as prior or concomitant, the medication will be classified by the worst case, i.e. concomitant.

- 'Prior' medications are medications which started and stopped prior to the study medication administration
- 'Concomitant' medications are medications which:
  - started prior to, on or after the study medication administration and started no later than 71 days following end of study medication,
  - AND ended on or after the study medication administration or were ongoing at the end of the study.

### 14. STUDY MEDICATION EXPOSURE

Exposure to study medication will be presented for the SAF. A listing with participants presented by treatment group, including the dosing dates and times, dose levels and dosing errors, if any, will be provided. A summary of exposure will be presented including the number of participants receiving the full dose, partial dose, and not receiving any dose by treatment, for all VIS954 treated participants, and for all participants combined.

### 15. PHARMACOKINETIC ANALYSIS

Pharmacokinetic concentration and parameter listings will include data for all treated participants. Descriptive statistic summaries and figures for PK analysis (serum) will be based on the PKAS. Summary statistics for PK concentrations and parameters will be presented for all participants in each dose level and by Japanese versus non-Japanese; Additionally, summary statistics for PK concentrations will be presented for all participants in each dose level and by ADA status (positive and negative). The summary statistics will include N, n, mean, SD, median, minimum, maximum, CV%. Geometric mean and geometric CV% will be presented for PK parameters, except for tmax for which only N, n, median, minimum, and maximum will be reported.

Visterra Insert
Customer Name/ Logo
Protocol VIS954-101
Page 25 of 42

Statistical Analysis Plan

